7.3.4 FINAL STUDY VISIT

Visit 11, Month 12 (\pm 14 days)

Subjects will return to the clinic seven months after the last assessment. Adverse events, vital signs and any changes to concomitant medications will be recorded. Subjects will complete a 5-point Likert satisfaction questionnaire and the POSAS.

Photographs of the treated area will be taken as described in section 7.3.1. The photographs will be sent to the blinded independent reviewer for assessment (GAIS, MSS and POSAS). The termination form will be completed and subjects will be discharged from the clinic and terminated from the study. The PI will

record all reportable events with start dates occurring any time after informed consent is obtained until 7 (for non-serious AEs) or 30 days (for SAEs) after the last day of study participation.

After the study is completed, subjects will be offered treatment on their untreated side (body/face).

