7.8 RESCUE MEDICATIONS, TREATMENTS, AND PROCEDURES

In the event that the subject experiences pain, the principal investigator may prescribe any analgesic deemed appropriate to the level of pain. If a subject experiences any first, second or third degree burn or pain beyond narcotics, then the following procedure will be implemented:

- Immediate triage and treatment of the patient shall be determined by the treating physician and based upon severity and type of burn identified.
- The event will be reported to the sponsor study Director within 24 hours of occurrence. If the event meets the criteria of a SAE, then it must be reported on the SAE form.
- An anonymized copy of the patient chart and treatment parameters are to be forwarded to the sponsor study Director within 24 hours.

The sponsor study Director will be responsible for issuing a written report to the company and the EC or IRB Chairman no later than 7 days from the event

Long term follow up and care shall continue at the discretion of the treating physician.

All patients experiencing a complication of the device will be followed a minimum of 2 years following the initial injury. Longer care and observation will be at the discretion of the treating physician.

All minor complications such as appearance or altered sensation, except for pain, can be reported within 30 days of patient complaint. Both chart and treatment parameters are to be provided to the study Director and shared with the company and EC or IRB chairman.

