8.3 TIME PERIOD AND FREQUENCY FOR EVENT ASSESSMENT AND FOLLOW-UP

The occurrence of an AE or SAE may come to the attention of study personnel during study visits and interviews of a study participant presenting for medical care, or upon review by a study monitor. All AEs including local and systemic reactions not meeting the criteria for SAEs will be captured on the appropriate CRF. Information to be collected includes event description, time of onset, clinician's assessment of severity, relationship to investigational device and study procedures (assessed only by those with the training and authority to make a diagnosis), and time of resolution/stabilization of the event. All AEs occurring while on study must be documented appropriately regardless of relationship. All AEs will be followed to adequate resolution.

Any medical condition that is present at the time that the participant is screened will be considered as baseline and not reported as an AE. However, if the study participant's condition deteriorates at any time during the study, it will be recorded as an AE.

Changes in the severity of an AE will be documented to allow an assessment of the duration of the event at each level of severity to be performed. AEs characterized as intermittent require documentation of onset and duration of each episode.

The PI will record all adverse events with start dates occurring any time after informed consent is obtained. At each study visit, the investigator will inquire study subjects about the occurrence of AE/SAEs since the last visit. All adverse events need to be followed until resolution or until study end, whichever occurs first.

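### Section 8.3 gives two incompatible stopping points for adverse events open at study end, and the earlier one falls 12 to 14 months short of the 2-year minimum in section 7.8

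*Combined protocol and SAP*

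**What the plan says.** Section 8.3 contains two rules for how long an AE is followed. The first is "All AEs will be followed to adequate resolution". The section closes with "All adverse events need to be followed until resolution or until study end, whichever occurs first". Study end is not defined. The same section lists "time of resolution/stabilization of the event" among the data to be collected, and has changes in severity documented "to allow an assessment of the duration of the event at each level of severity to be performed".

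Section 7.8 sets out a procedure triggered by a burn of any degree or by pain that narcotics do not control. It leaves long-term follow-up and care to the treating physician's judgement, and then says "All patients experiencing a complication of the device will be followed a minimum of 2 years following the initial injury". It adds that "Longer care and observation will be at the discretion of the treating physician". Its last paragraph says "All minor complications such as appearance or altered sensation, except for pain, can be reported within 30 days of patient complaint".

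On timing, section 3 gives 12 months of participation per subject and 15 months for the whole study (3 of enrolment, 12 of follow-up). At Visit 11 (Month 12), section 7.3.4 says that "subjects will be discharged from the clinic and terminated from the study". That section also has events recorded if they start up to 7 days (non-serious) or 30 days (serious) after the last day of participation. The schedule of events in section 7.3.7 ends at Visit 11.

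**The concern.** For an AE still open when the subject leaves, one sentence of section 8.3 requires follow-up to continue and the other ends it. For a device complication there is a second conflict. Section 8.1.1 makes any device-related event an AE, so sections 8.3 and 7.8 both apply to it. They give different stopping points, and neither section refers to the other.

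A site that relied on section 8.3 alone would stop too early for these subjects. Section 8.2.3 lists burns, pigment change and scarring as expected, and their late outcome matters. Early stopping would also cut short the recorded time to resolution and the duration by severity that section 8.3 itself calls for. Section 8.4.2 makes new findings on a reported serious AE (SAE) reportable, and a site that has stopped follow-up would not have them. Because the schedule ends at Visit 11, the 2-year follow-up also has no stated place to be recorded.

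**Working it through.** The plan gives no figure of its own to reproduce. The check compares the rules and then does date arithmetic on the stated schedule.

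**Rules side by side**

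| Situation | 8.3, uncapped sentence | 8.3, capped sentence | 7.8 (device complication) |
|---|---|---|---|
| Resolves before study end | Follow event to resolution | Follow event to resolution | Follow patient to 2 years |
| Open at study end | Continue | Stop | Follow patient to 2 years |

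The two 8.3 sentences agree in the first row and disagree in the second.

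**Inputs.** Treatments are at Day 0, Month 1 and Month 2 (sections 7.3.2 and 7.3.3). The minimum is 24 months from injury (7.8). Subject exit is at Month 12 (7.3.4). Enrolment lasts 3 months and the study 15 months (section 3). I assume that the injury occurs at a study treatment.

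**Gap after Visit 11.** Gap = injury month + 24 − 12. Share of the minimum = gap ÷ 24.

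| Injury at | 2-year point | Gap after Visit 11 | Share of 24 months |
|---|---|---|---|
| Day 0 | Month 24 | 12 months | 50% |
| Month 1 | Month 25 | 13 months | 54% |
| Month 2 | Month 26 | 14 months | 58% |

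Visit windows change this little. The shortest gap is 12 months − 14 days, about 11.5 months (Visit 11 late). The longest is 14 months + 7 + 14 days, about 14.7 months (third treatment late, Visit 11 early).

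**Other readings of study end**

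- Close of the whole study at calendar month 15. First subject, injury at Day 0: 0 + 0 + 24 − 15 = 9 months. Last subject, injury at Month 2: 3 + 2 + 24 − 15 = 14 months.
- Close of the section 7.3.4 recording window. Subtracting 7 days gives about 11.8 to 13.8 months (non-serious). Subtracting 30 days gives about 11.0 to 13.0 months (serious). That window governs when an event must start to be recorded, not how long it is followed, so it does not settle the matter.

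On none of these readings can an injury at a study treatment complete 2 years before study end.

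**Complications that resolve early.** Section 7.8 speaks of following patients. A subject whose complication resolves within weeks still attends the remaining visits to Month 12, with AEs asked about at each. For a completer, patient follow-up therefore falls short by the same 12 to 14 months as for an open event.

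**Effect on the planned analysis.** The AE endpoint runs to 10 months after the last treatment: Month 2 + 10 = Month 12, which is Visit 11. Section 10.4.4 plans counts of subjects with any AE, any SAE, or withdrawal from treatment due to an AE. None of these needs follow-up beyond Visit 11, and duration is not among them.

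**The case against.** The best defence is that section 7.8 is a rescue-care section. Its 2-year sentence comes after a trigger of burns or severe pain, counts from an injury, and directly follows a sentence leaving long-term follow-up to the treating physician. It could thus be a duty of care outside study data collection, limited to burns and severe pain. The later sentence of section 8.3 could likewise be read as qualifying the earlier one. These readings are possible, and the scope of 7.8 is ambiguous. But the 2-year sentence refers to all patients with a device complication, and no text limits it, takes it outside the study or sets precedence. On the narrowest scope the conflict still holds for burns. The protocol does say so when it wants follow-up past termination: under section 8.4.4 a subject who becomes pregnant is terminated, but the pregnancy is followed to its end.

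A reader might also infer more than the documents support:

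- *That almost all of the 2 years is lost when a complication resolves early.* For resolution at 3 weeks, that would be 730 − 21 = 709 of 730 days. This measures follow-up of the event, whereas 7.8 concerns the patient, who is still seen to Month 12.
- *That following section 8.3 necessarily breaches 7.8.* Section 8.3 does not forbid longer follow-up, and a site can satisfy both by also doing what 7.8 asks. The risk lies in relying on 8.3 alone.
- *That every minor complication already carries a 2-year duty.* The paragraph on minor complications sets only a reporting time.

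**Conclusion.** The point stands as a conflict between stated safety rules. Section 8.3 contradicts itself for AEs open at an undefined study end. Its capped rule stops 12 to 14 months (50% to 58%) short of the 2-year minimum in section 7.8 if study end is Visit 11, and 9 to 14 months short if it is the close of the study. These sizes assume an injury at one of the three treatments and a subject who completes to Month 12. An early leaver would fall further short. The conflict is certain for burns; how much further it extends depends on the unstated scope of 7.8. The documents give no complication rate, so the number of subjects affected cannot be estimated.

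The effect is on safety follow-up and late outcomes. A reader should not infer that the 10-month AE endpoint or the section 10.4.4 counts are compromised; neither is affected.

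**What to change.** Replace both follow-up sentences in section 8.3 with one rule, for example:

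> An AE is followed until it resolves or stabilizes, or until the subject's study end (Visit 11 or early exit) if that comes sooner, with two exceptions. (a) Every SAE, whatever its relationship to the device and including any that starts in the 30-day window of section 7.3.4, and every device-related AE open at exit, is followed until it resolves or stabilizes. (b) A subject with a device complication under section 7.8 is followed for at least 2 years from the injury. Where the sections differ, section 7.8 prevails.

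Exception (a) needs to cover unrelated SAEs, because section 8.4.2 makes updates reportable for any SAE and the uncapped sentence being replaced is the only one that now covers them after exit.

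In section 7.8, state which complications trigger the 2-year minimum. These should include at least burns and pain beyond narcotic control, and exclude the transient erythema and edema that section 7.3.2 treats as normal. Also state where follow-up after Visit 11 is recorded.

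The cost is wording, a CRF instruction, contacts after Month 12 for the subjects concerned, and a short late-outcome update to the report. The contacts under (b) are already required by section 7.8; those under (a) may be additional. The Month 12 report need not wait. The consent pages were not available for this review, so the sponsor should check that they allow contact after Month 12.

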8.4 REPORTING PROCEDURES

8.4.1 ADVERSE EVENT REPORTING

All AEs will be recorded on the appropriate CRF and will include information about the start and stop dates, severity and relatedness. There should be an attempt to report a "diagnosis" rather than the individual signs, symptoms and abnormal laboratory values associated with the diagnosis. However, a diagnosis should be reported only if, in the Investigator's judgment, it is relatively certain (i.e., definite or possible). Otherwise individual signs, symptoms and abnormal laboratory values should be reported as distinct adverse events.

8.4.2 SERIOUS ADVERSE EVENT REPORTING

All serious AE, whether or not deemed procedure or device related, must be reported to the sponsor's clinical research department immediately or within 24 hours by telephone or by email (see contact details below).

[REDACTED]

[REDACTED]

[REDACTED]

[REDACTED]

A written report prepared by the Principal Investigator (or designate) must follow within seven working days to the clinical monitor and should include a full description of the event and sequence.

The study investigator shall complete a Serious Adverse Event / Serious Adverse Device Effect Form and submit to the study sponsor as soon as possible, but in no event later than 10 working days after the investigator first learns of the effect.

In accordance with the requirements of Directive 93/42/EEC, and with MEDDEV 2.7/3, the following events are considered reportable events:

1. any SAE (whether or not study procedure or device related),
2. any Investigational Medical Device Deficiency that might have led to a SAE if a) suitable action had not been taken or b) intervention had not been made or c) if circumstances had been less fortunate,
3. new findings/updates in relation to already reported events.

The sponsor will report the above-mentioned events to the Competent Authorities of all countries where the study is being conducted, within the following timelines:

- Any SAE which indicates an imminent risk of death, serious injury, or serious illness AND that requires prompt remedial action for other patients/subjects, users or other persons or a new finding to it: immediately, but not later than 2 calendar days after awareness by sponsor of a new reportable event or of new information in relation with an already reported event.
- Any other reportable event or a new finding / update to it: immediately, but not later than 7 calendar days following the date of awareness by the sponsor of the new reportable event or of new information in relation with an already reported event.

Reporting of the events listed above (under bullets 1-3) to the ECs of the participating sites and to the other investigators will be performed according to country and/or site-specific requirements.

8.4.4 REPORTING OF PREGNANCY

If a subject becomes pregnant during the course of the study, the subject will be terminated from the study. The pregnancy will be immediately reported to the sponsor on the Notification of Subject or Partner Pregnancy form using the same reporting timelines as a SAE. The investigator will follow the pregnancy until completion and will report the outcome of the pregnancy to the sponsor on the Notification of Subject or Partner Pregnancy Outcome form within 10 business days.

8.5 STUDY HALTING RULES

The study may be halted at any time by the sponsor, the EC / IRB, Competent Authorities due to safety concerns. Examples of findings that might trigger a safety review are the number of SAEs overall, the number of occurrences of a particular type of SAE, severe AEs/reactions, or increased frequency of events. If the study is halted, the sponsor will immediately notify all investigational sites, the EC / IRB(s), the Competent Authorities of all countries where the study is being conducted.

8.6 SAFETY OVERSIGHT

Independent oversight is an important component to ensure human subjects' protection. Safety oversight will be under the direction of the sponsor and a medical monitor.

8.7 TRAINING REQUIREMENTS

Prior to patients' enrollment, the Sponsor will provide training relevant and pertinent to the involvement of personnel conducting study activities. Training for investigators and staff will include study-specific protocol and CRF completion training by the sponsor or designate and on-site training on the use of the investigational device by the sponsor. Evidence of training will be documented during the site initiation visit and by the issuance of a device training certificate.

9 CLINICAL MONITORING

Clinical site monitoring is conducted to ensure that the rights and well-being of human subjects are protected, that the reported trial data are accurate, complete, and verifiable, and that the conduct of the trial is in compliance with the currently approved protocol/amendment(s), with GCP, and with applicable regulatory requirement(s).

- Monitoring for this study will be performed by the sponsor or designate.
- On-site monitoring will occur within 4 weeks of first enrolled subject and will occur at a frequency described in the Monitoring Plan.
- Variables to be monitored will be described in the Monitoring Plan.
- The Study Director or designate will be provided copies of monitoring reports within 15 business days of visit.

10 STATISTICAL CONSIDERATIONS

10.1 STATISTICAL AND ANALYTICAL PLANS

The Statistical and Analytical Plan (SAP) may be revised during the study to accommodate Clinical Trial Protocol Amendments and to make changes to adapt to unexpected issues in study execution and data that affect planned analyses. If revised, a formal Statistical and Analytical Plans (SAP) will be completed and issued prior to database lock and unblinding of the study data if applicable.

10.2 STATISTICAL HYPOTHESES

The null and alternative hypotheses for the study's primary, key secondary and safety endpoints are;

- Primary Performance Endpoint:
 - **Null Hypothesis ($H_0: \mu_d = \mu_{post} - \mu_{pre} = 0$)** – There is no improvement of surgical scars at 3 months post-treatment review compared to baseline.
Alternative Hypothesis ($H_a: \mu_d = \mu_{post} - \mu_{pre} \neq 0$) – There is improvement of surgical scars at 3 months post-treatment review compared to baseline. The improvement of surgical scars will be defined by General Aesthetic Improvement Scale (GAIS) and Manchester Scar Scale (MSS) scores evaluated by independent blinded reviewer. Expected mean improvement difference is not less than one (1) GAIS and MSS score higher than baseline.
 - **Null Hypothesis ($H_0: \mu_d = \mu_{post} - \mu_{pre} = 0$)** – There is no improvement of surgical scars at 10 months post-treatment review compared to baseline.

Alternative Hypothesis ($H_a: \mu_d = \mu_{post} - \mu_{pre} \neq 0$) – There is improvement of surgical scars at 10 months post-treatment review compared to baseline. The improvement of surgical scars will be defined using General Aesthetic Improvement Scale (GAIS) and Manchester Scar Scale (MSS) scores evaluated by independent blinded reviewer. Expected mean improvement difference is not less than one (1) GAIS and MSS score higher than baseline.

- Secondary Performance Endpoint(s):
 - **Null Hypothesis ($H_0: \mu_d = \mu_{post} - \mu_{pre} = 0$)** – There is no improvement of surgical scars at 1 and 2 months post-treatment review compared to baseline.
Alternative Hypothesis ($H_a: \mu_d = \mu_{post} - \mu_{pre} \neq 0$) – There is improvement of surgical scars at 1 and 2 months post-treatment review compared to baseline. The improvement of surgical scars will be defined using General Aesthetic Improvement Scale (GAIS) and Manchester Scar Scale scores evaluated by independent blinded reviewer.
 - **Null Hypothesis ($H_0: \mu_d = \mu_{post} - \mu_{pre} = 0$)** – There is no improvement of surgical scars at 3 and 10 months post-treatment review compared to baseline.
Alternative Hypothesis ($H_a: \mu_d = \mu_{post} - \mu_{pre} \neq 0$) – There is improvement of surgical scars at 3 and 10 months post-treatment review compared to baseline. The improvement of surgical scars will be defined using Patient and Observer Scar Assessment Scale (POSAS) scores evaluated by independent blinded reviewer.
 - **Null Hypothesis ($H_0: \mu_d = \mu_{post} - \mu_{pre} = 0$)** – There is no improvement of surgical scars at 3 and 10 months post-treatment review compared to baseline.
Alternative Hypothesis ($H_a: \mu_d = \mu_{post} - \mu_{pre} \neq 0$) – There is improvement of surgical scars at 3 and 10 months post-treatment review compared to baseline. The improvement of surgical scars will be defined using Patient and Observer Scar Assessment Scale (POSAS) scores evaluated by the subject.
 - **Null Hypothesis ($H_0: \mu_d = \mu_{post} - \mu_{pre} = 0$)** – There is no satisfaction with treatment as documented on a 5-point Likert scale at 3 and 10 months compared to baseline.
Alternative Hypothesis ($H_a: \mu_d = \mu_{post} - \mu_{pre} \neq 0$) – There is satisfaction with treatment as documented on a 5-point Likert scale at 3 and 10 months compared to baseline. The satisfaction with treatment will be defined by 5-point Likert scale at 3 and 10 months compared to baseline as assessed by the subjects.
- Safety Endpoint:
 - **Null Hypothesis ($H_0: \mu_d = \mu_{post} - \mu_{pre} = 0$)** – There is no difference in subjects' 10 cm discomfort/pain VAS score experienced after at Visit 6 treatment and that of baseline treatment (Visit 2).
Alternative Hypothesis ($H_a: \mu_d = \mu_{post} - \mu_{pre} \neq 0$) – There is a difference in subjects' 10 cm discomfort/pain VAS score experienced after at Visit 6 treatment and that of baseline treatment (Visit 2). Expected mean difference is maximum VAS score ≤ 1 .

